4.2 Analysis Methods

4.2.1 Demographics and Baseline Characteristics

4.2.1.1 Subject Disposition

Subject disposition will be summarised using all enrolled subjects (enrolled analysis set). Percentages will be calculated based on the number of subjects assigned to treatment.

The number of subjects enrolled, and the number and percentage of subjects received study treatment, did not receive study treatment, completed study, and prematurely withdrawn from study (including reason) will be presented. Study discontinuation reasons are detailed in CSP Section 7.2. The number of subjects withdrawing from study due to pandemic or other global country situations will be summarised as well. Reasons for prematurely withdrawing from study will also be listed.

A listing of all subjects impacted by pandemic or other global country situations disruptions will be produced with details of changed or missed visits.

The number and percentage of subjects included and excluded from each analysis set will be summarised, including the reason for exclusion from each analysis set. Important protocol

deviations will also be provided in a separate table and listed for the safety analysis set. In addition, a listing of all COVID-19 related protocol deviations (important and non-important) will be provided.

4.2.1.2 Demographics and Other Baseline Characteristics

Demographics and subject characteristics will be summarised using frequencies and percentages (for categorical variables sex, race and ethnic group) and descriptive statistics (for continuous variables age, height, weight and BMI) using both the PK and safety analysis set.

Various baseline characteristics will also be summarised for all subjects in the safety analysis set. These include relevant medical and surgical histories, spirometry lung function data at screening such as **CCI** [REDACTED] at baseline, and respiratory disease characteristics including asthma duration, age at onset of asthma, the number of exacerbations in the previous 6 months, and the number of exacerbations requiring hospitalisations in the previous 6 months.

Relevant medical and surgical histories will be summarized by MedDRA Preferred Term (PT) within the System Organ Class (SOC) level of MedDRA.

4.2.2 Prior and Concomitant Medications

The number and percentage of subjects taking maintenance asthma medications such as ICS/long acting beta agonist (LABA) fixed dose combinations, at baseline will be summarised. For those subjects taking ICS at baseline the converted dose units will also be summarised. The details concerning dose conversions for ICS are provided in the Appendix H of the CSP. The number of subjects treated with ICS at baseline will be summarised by ATC code and preferred term, with total daily dose (non-converted) at baseline summarised for each preferred term.

Disallowed medications will include medications defined as prohibited according to Section 6.5.2 of the CSP. They will be defined following a physician review (prior to database lock) of the unique combinations of Anatomical Therapeutic Chemical (ATC) code classifications and generic terms captured.

Separate tables will be presented for all allowed and disallowed medications received during each of the following study periods: screening period and on-study period respectively.

Prior and concomitant medications will be listed for the safety analysis set, including allowed and disallowed medications.

4.2.3 Exposure to Investigational Product

The number and percentage of subjects who received IP will be summarised. Exposure data will be summarised and listed for the safety analysis set.

4.2.4 Pharmacokinetics

All PK analyses will be based on the PK analysis set.

4.2.4.1 Handling of Missed PK Sample Collections

Data from subjects that have missing PK sample(s) will be included in concentration-time listings, individual PK profile plots and associated summary statistics. Available PK parameters will be included in the PK parameter listing and associated summary statistics.

4.2.4.2 Serum Concentration Data

All tezepelumab serum concentration data received will be listed by subject, and summaries will be presented by nominal time in days (calculated as Study Day minus 1), for subjects included in the PK analysis set. A listing of PK blood sample collection times as well as derived sampling time deviations will be provided. The individual serum tezepelumab concentrations will be plotted versus actual elapsed time of PK sampling relative to dosing time in days; the geometric mean (together with confidence intervals derived as geometric mean multiplied or divided by geometric SD) of serum tezepelumab concentrations will be plotted versus nominal time; the y-axis will be presented on both a linear and a log-scale.

Serum concentrations below the lower limit of quantification (LLOQ) will be handled as follows for descriptive statistics:

- At a time point where 50% or less of the values are below the LLOQ (BLQ), all BLQ values will be set to $\frac{1}{2}$ LLOQ, and all descriptive statistics will be calculated. The maximum value will be reported from the individual data, and the minimum will be reported as $\frac{1}{2}$ LLOQ.
- At a time point where more than 50%, but not all, of the values are BLQ, the mean, SD, geometric mean, and CV% will be reported as 'Not Determined' (ND). The maximum value will be reported from the individual data, and the minimum and median will be reported as BLQ.
- If all the concentrations are BLQ, the geometric mean and mean, and the minimum, median, and maximum will be reported as BLQ, and the SD, CV%, and GCV% as ND.
- The number of BLQ values (n below LLOQ) will be reported for each time point.

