9.2 Sample Size Determination

No formal sample size calculation was conducted for this study. The number of subjects was based on the desire to obtain adequate PK and safety data while exposing as few paediatric subjects as possible to tezepelumab and study procedures. A total of 12 subjects is considered sufficient to provide adequate data to characterise PK of tezepelumab in children aged ≥ 5 to 11 years. At least 4 subjects will have body weight < 25 kg and a minimum of 3 subjects will have body weight ≥ 25 kg and < 40 kg. Approximately 14 subjects will receive tezepelumab in an attempt to have at least 12 subjects complete the study.

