9.4.2 Efficacy

9.4.2.1 Primary Endpoints

All PK analyses will be based on the PK analysis set. Tezepelumab serum concentration data will be listed by individual and summarised by nominal time using descriptive statistics, including N, geometric mean, geometric CV%, arithmetic mean, arithmetic SD, median, minimum and maximum. The mean and individual serum tezepelumab concentrations will be plotted over time. Based on the serum concentration-time data of tezepelumab, the following PK parameters will be estimated using noncompartmental analysis method as appropriate: $AUC_{0-\infty}$, $AUC_{0-\text{last}}$, C_{\max} , t_{\max} , terminal $t_{1/2}$, CL/F and V_{ss}/F . Additional PK parameters may be reported if appropriate. PK parameters will be listed by individual and summarised using descriptive statistics. The PK analysis will be performed using WinNonlin® version 5.1 or higher.

The PK data obtained in this study may be included in a population PK analysis, as appropriate, to assess any PK differences between children aged ≥ 5 to 11 years and adults/adolescents, and guide dosing for future studies of tezepelumab in paediatric subjects. If conducted, this analysis will be reported separately from the CSR.

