4 ANALYSIS METHODS

4.1 General Principles

The analyses will be performed by IQVIA using the SAS® (Statistical Analysis Software; SAS Institute, Inc., Cary, North Carolina) statistical software system version 9.4 or higher. All analyses will be performed according to AZ standard operating procedures unless otherwise stated herein.

After the last subject has completed their Visit 9, the database for the study will be locked and the data will be reported in a CSR.

All individual data as recorded in the final study database, after the last subject has completed their Visit 9, will be provided by IQVIA Data Management.

No formal statistical hypothesis tests will be made. Data will be provided in data listings sorted by subject number. Tabular summaries will be presented.

For qualitative variables and categorical data, the population size (N), number of patients with available data (n), and the percentage (of available data) for each class of the variable will be presented. Percentages will be rounded to 1 decimal place.

Quantitative data, including PK data, will be summarised using descriptive statistics, including N, n, mean, standard deviation (SD), 1st quartile (Q1), median, 3rd quartile (Q3), minimum (min), and maximum (max), unless stated otherwise.

Additionally, coefficient of variation (CV%), geometric mean, geometric SD, and geometric coefficient of variation (GCV%) will be reported for PK concentrations and parameters, except t_{max} which will be summarized using n, median, min and max. These results will be presented in tables and figures as applicable.

Geometric mean is calculated as $\exp[\mu]$, where μ is the mean of log-transformed data.

GCV% is calculated as $100 \sqrt{[\exp(s^2) - 1]}$, where s is the SD of log-transformed data.

For non-PK data the mean, median, and first and third quartiles (where applicable) will be presented with one more decimal place than the raw data, the SD will be presented with two more decimal places than the raw data, and min and max values will have the same number of decimal places as the raw data.

For all serum concentrations and PK parameters for tezepelumab, data and descriptive statistics will be presented in summary tables and by-subject listings as described in [Table 3](#), but the calculation of summary statistics will be performed using unrounded data.

Table 3 **Conventions for Reporting of Pharmacokinetic Data**

Variable/ Parameter	Data in Listings	Reporting in Summary Tables			

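### SAP 4.2.4.2 calls geometric mean ×/÷ geometric SD a confidence interval on the mean concentration plot, but it is a one-SD between-subject spread

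*SAP*

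**What the plan says.** SAP 4.2.4.2 asks for a figure of the geometric mean serum concentration against nominal time, on linear and log y-axes, with "confidence intervals derived as geometric mean multiplied or divided by geometric SD". It gives no confidence level.

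SAP 4.1 supplies the ingredients. The geometric mean is exp(μ), where μ "is the mean of log-transformed data". The GCV% formula uses s, "where s is the SD of log-transformed data". Geometric SD has no formula of its own and appears only among the descriptive statistics: "geometric SD, and geometric coefficient of variation (GCV%) will be reported for PK concentrations and parameters".

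Protocol 9.4.2.1 asks for the plot without any interval: "The mean and individual serum tezepelumab concentrations will be plotted over time". The SAP sentence is therefore the only definition of the bars.

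**The concern.** The sentence names one quantity and gives the formula of another. A confidence interval describes how precisely the geometric mean is estimated and shrinks as subjects are added. Geometric mean ×/÷ geometric SD describes how much children differ from one another and settles to a fixed width however many are studied.

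Describing the PK is the primary objective, and this is the SAP's mean concentration-time figure. A reader who takes the label at face value would overstate the uncertainty of the geometric mean. The specification is also ambiguous: a programmer guided by the name could draw a true confidence interval, and one guided by the formula would draw a spread.

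**Working it through.** The plan states no width, level or precision for these bars, so there is no figure of its own to reproduce. The check compares the formula as written with a confidence interval of the geometric mean.

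**Inputs**

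- Bars: geometric mean ×/÷ geometric SD (SAP 4.2.4.2).
- m and s: mean and SD of the log concentrations at a time point (SAP 4.1, where the mean is written μ).
- Geometric SD = exp(s). This is an assumption, the standard meaning, because the SAP gives no formula.
- n = 12 to 14, from Protocol 9.2: "Approximately 14 subjects will receive tezepelumab in an attempt to have at least 12 subjects complete the study".
- Confidence level: not stated. 95% two-sided is assumed, with 90% and 99% as a range.

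**Step 1: what the bars are.** exp(m) ×/÷ exp(s) = exp(m ± s). The half-width on the log scale is s. Neither n nor a quantile appears.

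**Step 2: what a confidence interval would be.** The 95% interval of the geometric mean is exp(m ± t(0.975, n−1) × s/√n). The half-width on the log scale is t × s/√n.

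**Step 3: ratio of log-scale widths.** s ÷ (t × s/√n) = √n/t. The SD cancels, so the log-scale ratio does not depend on the CV.

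| n | √n | t(0.975, n−1) | Ratio to 95% CI | Ratio to 90% CI |
|---|---|---|---|---|
| 12 | 3.464 | 2.201 | 1.574 | 1.929 |
| 13 | 3.606 | 2.179 | 1.655 | 2.023 |
| 14 | 3.742 | 2.160 | 1.732 | 2.113 |

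Against a 99% interval the ratios are 3.464/3.106 = 1.12 (n = 12) and 3.742/3.012 = 1.24 (n = 14).

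**Step 4: the linear axis.** The width ratio there is sinh(s)/sinh(t × s/√n), which depends on s. For illustration, the adolescent single-dose study in Protocol 2.2 reports a Cmax of 24.0 ± 6.59 µg/mL:

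- CV = 6.59/24.0 = 0.275; under log-normality s = √ln(1 + CV²) = 0.270 and geometric SD = 1.31.
- The SAP bars run from 0.764 to 1.309 times the geometric mean, whatever n is.
- The 95% interval runs from 0.843 to 1.187 times it (n = 12) or 0.856 to 1.168 (n = 14).
- The linear width ratios are 1.59 (n = 12) and 1.75 (n = 14).

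**Step 5: the level the bars would have as a confidence interval.** Assuming log-normal concentrations, the level is 1 − 2P(t(n−1) > √n): 99.5% (n = 12), 99.6% (n = 13), 99.8% (n = 14).

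**Step 6: what the bars cover as a spread.** Also under log-normality, the chance that a new child falls inside is 1 − 2P(t(n−1) > 1/√(1 + 1/n)): 64.3% (n = 12) to 64.8% (n = 14).

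**Step 7: fewer samples.** At n = 10 the 95% ratio is 3.162/2.262 = 1.40. This can arise because the summaries keep incomplete profiles: "Data from subjects that have missing PK sample(s) will be included in concentration-time listings", and likewise in the associated summary statistics.

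**The case against.** The best defence is that the sentence discloses its own formula. Anyone with the SAP can see what will be drawn, and harm needs that formula to be lost from the final figure, whose footnotes are not in the documents. The tables give n, geometric mean and geometric SD, and individual profiles are plotted and listed, so a reader can work out a proper interval. The error is in the cautious direction, since the mean looks less precise than it is. Showing between-subject spread is also legitimate in a descriptive PK study.

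Most of this stands, and it limits how much the point matters. It does not make the label right: the formula and the name cannot both be followed, and no other text chooses between them.

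The 1.57 to 1.73 figure also has conditions, and these stand too. It is a log-scale ratio against an assumed 95% level at 12 to 14 subjects. It changes with the level, is slightly larger on the linear axis at the adolescent variability, and falls with fewer samples. The bars do not exist at every time point either: SAP 4.2.4.2 gives no numeric geometric mean where more than half the values are below the quantification limit.

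**Conclusion.** The point holds. The bars defined in SAP 4.2.4.2 are a one-SD between-subject spread and are wrongly called confidence intervals. With 12 to 14 children they are 1.57 to 1.73 times as wide, on the log scale, as a 95% confidence interval of the geometric mean.

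This rests on reading geometric SD as exp(s) and on the assumed 95% level. The log-scale ratios need no distributional assumption; the implied levels and the new-child coverage need log-normality.

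The sentence should be corrected, but the consequence is confined to one descriptive figure. The tabulated geometric mean, geometric SD and GCV% are unaffected. No hypothesis test is planned, and the Day 29 dose-confirmation text (SAP 4.2.4.3 and 6) states no criterion that uses these bars.

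**What to change.** Choose one and state it in SAP 4.2.4.2 and in the figure footnote:

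1. **Keep the formula and change the name.** Label the bars *geometric mean ×/÷ geometric SD (between-subject spread)*. This is enough to remove the error.
2. **Keep the name and change the formula.** Plot exp(m ± t(0.975, n−1) × s/√n), with n counted at each time point, and label it *95% CI of the geometric mean*. Equivalently, raise the geometric SD to the power t/√n, which is 2.201/3.464 = 0.635 at n = 12 and 2.160/3.742 = 0.577 at n = 14.

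Under either option, add that geometric SD means exp(s).

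The cost is one SAP sentence and one footnote; option 2 also needs the plotted limits recalculated. Neither needs new data or changes a table. Printing the 95% interval of the geometric mean in the PK parameter table would be a useful extra, but it is not needed to correct this error.

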4.2.4.3 Pharmacokinetic Parameters

Any BLQ concentrations will be assigned a value of zero if they precede quantifiable samples in the initial portion of the profile. BLQ values that occur at any other time points are treated as missing and excluded from the PK analysis for the calculation of PK parameters.

If two or more consecutive BLQ concentrations are followed by quantifiable concentrations in the terminal portion of the concentration curve, these quantifiable values will be excluded

from the PK analysis for the calculation of PK parameters, unless otherwise warranted by the concentration-time profile.

The following PK parameters will be estimated, if appropriate, using noncompartmental analysis method performed using WinNonlin® version 8.0 or higher. The actual elapsed sampling times will be used in the final PK parameter calculations. A minimum of 3 quantifiable concentration-time data points will be required for calculation of PK parameters.

The following PK parameters, as appropriate based on the data, will be listed by subject and summarised using descriptive statistics:

- $AUC_{0-\infty}$,
- $AUC_{0-\text{last}}$,
- C_{\max} ,
- t_{\max} ,
- $t_{1/2}$,
- CL/F ,
- V_{ss}/F ,
- V_z/F .

The following PK parameters will be calculated for diagnostic purposes and listed but not summarised:

- λ_z , N Number of data points included in the log-linear regression analysis to determine λ_z . A minimum of 3 data points will be used for determination.
- Rsq Goodness of fit statistic for calculation of λ_z . If the Rsq is <0.800 , then λ_z and related parameters will be flagged.
- t_{last} Time of the last postdose quantifiable serum concentration.
- %AUCex Percentage of $AUC_{0-\infty}$ obtained by extrapolation, calculated as $[(C_{\text{last}}/\lambda_z)/AUC_{0-\infty} * 100]$. If the %AUCex is greater than 30.0% of $AUC_{0-\infty}$, then $AUC_{0-\infty}$ and related parameters will be flagged.

Note: parameters will be included in summary statistics unless they are deemed necessary to exclude due to protocol deviations. The PK data obtained in this study may be included in a population PK analysis, as appropriate, to assess any PK differences between children aged ≥ 5 to 11 years and adults/adolescents, and guide dosing for future studies of tezepelumab in paediatric subjects. If conducted, this analysis will be reported separately from the CSR.

Day 29 PK analysis results will be evaluated after last subject has completed their visit on Day 29 (Visit 7) to confirm the dose of tezepelumab selected for future safety and efficacy study in 5 to <12 years old children.

4.2.5 Immunogenicity

All listings and summaries of ADA results will be based on the safety analysis set.

Immunogenicity of tezepelumab (ADA) results will be listed by subjects with any positive ADA result at any time first, followed by subjects with no positive ADA result by scheduled visit. The corresponding titre summaries (e.g. 1st quartile, median, 3rd quartile) of each ADA category will be provided, and will be based on the maximum titre of all positive samples for each subject.

The ADA status across the study for each subject will also be classified and listed as per the following categories:

- Subjects who are ADA positive at any time including baseline and/or post-baseline (ADA prevalence).
- Subjects who are ADA positive at baseline only.
- Subjects who are ADA positive at baseline and positive in at least one post baseline measurement.
- Subjects who are ADA positive at baseline regardless of post-baseline result.
- Subjects who are ADA positive post-baseline.
- Subjects who are ADA positive post-baseline and ADA negative at baseline (treatment induced ADA positive)
- Subjects who are treatment boosted ADA positive, defined as baseline positive ADA titre that was boosted to a 4 fold or higher level following IP administration
- Subjects who are treatment emergent ADA (TE-ADA) positive (ADA incidence): defined as either treatment induced ADA positive or treatment boosted ADA positive.

4.2.5.1 Potential effects of ADA on PK

The impact of ADA on PK will be explored using the PK analysis set.

The impact of ADA on PK will be explored by comparing individual serum tezepelumab concentration time profiles in ADA positive (any time) and ADA negative subjects.

4.2.5.2 Potential effects of ADA on Safety

Impact of ADA on AEs may be evaluated as appropriate.

4.2.6 Safety

All safety and tolerability variables will be summarised and evaluated descriptively using the safety analysis set. Out-of-range values for safety laboratory and vital signs (based on paediatric reference values provided in Table 2 of SAP) will be flagged in individual listings.

Safety data will be reported using the safety analysis set. Safety data will be presented using descriptive statistics unless otherwise specified.

4.2.6.1 Adverse Events

All AEs experienced by the subjects will be collected throughout the study, as per CSP Table 1, and will be coded by IQVIA using the latest version of MedDRA at the time of database lock.

Adverse events and SAEs will be categorised for analysis according to their onset date into occurring during the screening period or the on-study period. Adverse events occurring during the screening period will only be presented in the subject listing. Adverse events occurring during the on-study period will be summarised and listed as follows:

An overall summary table will be produced showing the number and percentage of subjects with at least one AE in each of the following categories: any AEs, SAEs, AEs with outcome of death, and AEs leading to withdrawal from study. The total number of AEs in the different AE categories in terms of AE counts will also be presented (i.e. accounting for multiple occurrences of the same event in a subject).

Adverse events, SAEs, AEs with outcome of death, AESIs and AEs leading to withdrawal from study will be summarised by SOC and PT assigned to the event using the MedDRA dictionary by descending frequency order. For each PT, the number and percentage of subjects reporting at least one occurrence of the event will be presented (i.e. subjects with multiple occurrences of the same PT will only be counted once).

Adverse events and SAEs will be summarized by PT and Investigator's causality assessment (related versus not related) and maximum intensity. If a subject reports multiple occurrence of the same AE within the same reported period, the maximum intensity will be taken as the highest recorded maximum intensity (the order being severe, moderate, and mild).

Separate listings of subjects with AEs, SAEs, AEs with outcome of death and AEs leading to withdrawal from study will be presented.

